### 3.5 Pharmacodynamic Assessment

The secondary endpoints concern the pharmacodynamics of LBP-EC01. These will be summarized by treatment based on the PD Population.

*E. coli* assessments will be made at the timepoints specified in the SoA of the protocol. Incidence of the following endpoints will also be summarized with counts and percentages of patients at Day 1 (Baseline), Day 2, Day 3, Day 5, Day 7 (EOT), Day 14 and Day 28:

- Reduction in urinary *E. coli* burden at timepoint from Baseline
- Biological elimination of *E. coli* at timepoint after Baseline. Biological elimination is defined as measurement below  $1 \times 10^3$  CFU/mL

The following *E. coli* parameters will be derived based on all available post-Baseline data and summarized and listed:

- Time to 1 log reduction in urinary *E. coli* from Baseline
- Biological elimination at any timepoint.
- Incidence and time to recurrence of *E. coli* colonization. Recurrence is defined as past biological elimination followed by increase above the patient's baseline CFU/mL.
- Incidence of infection based on clinical signs and symptoms defined as an adverse event marked as a UTI symptom and followed by antibiotic use.

*E. coli* parameters will be summarized first for the total CFU/mL in a patient (sum of CFU/mL for all *E. coli* strains) but may also be summarized by strain specific *E. coli* colonization (individual strain CFU/mL per patient).

All *E. coli* assessment data will be listed.

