### *3.1.4 Summary Statistics*

Categorical data will generally be summarized with counts and percentages of patients. The denominator used for the percentage calculation will be clearly defined. Continuous data will generally be summarized with descriptive statistics including n (number of non-missing values), mean, median, standard deviation, minimum, and maximum. Geometric mean (GM), and GM CV% will also be provided for PK parameters. The value of zero will be excluded from the calculation of GM and GM CV%.

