### 3.2.5 *PD Population*

The PD Population is defined as all randomized patients who met enrollment criteria, who receive at least one dose of study drug, have a baseline PK assessment, and have a baseline *E. coli* measurement at or above  $1 \times 10^3$  Colony-Forming Unit (CFU)/mL. The PD Population will be the primary population for analysis of all PD-related secondary and exploratory endpoints.

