#### 3.6.1 *Urine Culture and Sensitivity*

Urine culture and sensitivity assessments will be made at the timepoints specified in the SoA of the protocol. Incidence and summaries of CFU/mL levels of all non-*E. coli* bacteria isolated will be presented at each scheduled visit. Overall summaries of all bacteria (including *E. coli*) may also be presented. All data will be listed.

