#### 3.7.2.1 Hematology, Chemistry, Coagulation, Lipids, and Urinalysis

Values and changes from baseline will be presented at each scheduled visit and baseline by laboratory test. The incidence of abnormalities (as defined by normal ranges) prior to the first dose of study drug and after the first dose of study drug will be summarized with counts and percentages of patients. Data will be listed.

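### Section 3.5 names by-visit E. coli reduction only as an incidence with no minimum fall, and nowhere does the SAP commit to log10 CFU/mL or its change from baseline

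*SAP*

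**What the plan says.** SAP section 3.5 holds the placebo-controlled read-out of activity against E. coli. These endpoints are secondary, and section 3.1.5 plans no hypothesis test.

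- **By-visit endpoints.** At baseline and on Days 2, 3, 5, 7, 14 and 28: "Incidence of the following endpoints will also be summarized with counts and percentages of patients". Two endpoints follow. Reduction from baseline has no size attached. Biological elimination has a cut-off of 1 x 10^3 CFU/mL. Section 2.3.2 gives no size for reduction either.
- **Derived endpoints.** Time to 1 log reduction, elimination at any time, recurrence and infection: these E. coli "parameters will be derived based on all available post-Baseline data and summarized and listed". Infection is defined as "an adverse event marked as a UTI symptom and followed by antibiotic use".
- **Quantity analysed.** The E. coli "parameters will be summarized first for the total CFU/mL in a patient", that is, the sum over strains. This fixes the quantity but names no statistic, log scale or change from baseline.
- **General rule.** Section 3.1.4 gives n, mean, median, SD, minimum and maximum for continuous data, and then: "Geometric mean (GM), and GM CV% will also be provided for PK parameters".
- **Population.** Section 3.2.5: "The PD Population will be the primary population for analysis of all PD-related secondary and exploratory endpoints".

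Other measurements get more. For laboratory tests, section 3.7.2.1 states: "Values and changes from baseline will be presented at each scheduled visit and baseline by laboratory test". Sections 3.7.3, 3.7.4, 3.7.6 and 3.7.8 commit to the same for immunoglobulins, vital signs, ECG and spleen size. Section 3.6.1 says that incidence and CFU/mL levels of non-E. coli "bacteria isolated will be presented at each scheduled visit". It leaves an overall summary that includes E. coli optional, and section 3.6 places it on the ITT and Evaluable Populations.

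**The concern.** Bacterial counts span orders of magnitude, so a reader wants to know how far the count fell, in log10 units, in each arm at each visit. The one by-visit summary of reduction that section 3.5 names answers a weaker question: how many patients had a lower value than at baseline. Measurement noise alone produces such a value about half the time.

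If a continuous summary is produced under section 3.1.4, nothing puts it on a log scale or expresses it as change from baseline. A mean of raw CFU/mL in an arm of about 12 says mostly what one or two heavily colonized patients did. The trial could then report its activity result without stating the size of the effect, although the data to do so are collected.

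**Working it through.** **Inputs.** From the SAP: 36 patients at 2:1 (section 2.2.4), so 36 x 2/3 = 24 and 36/3 = 12; PD Population entry at 1 x 10^3 CFU/mL (section 3.2.5); the 1 log threshold (section 3.5). The SAP gives no SD, mean or effect size, so there is no figure of its own to reproduce. All SDs and means below are assumptions.

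**1. Any-fall rate at one visit.** If the change in log10 CFU/mL is normal with mean fall m and standard deviation SD, then P(any fall) = Phi(m/SD) and P(fall >= 1 log10) = Phi((m - 1)/SD). With SD = 1:

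| True mean fall (log10) | Any fall | Fall >= 1 log10 |
|---|---|---|
| 0 | 50% | 16% |
| 0.5 | 69% | 31% |
| 1 | 84% | 50% |
| 2 | 97.7% | 84% |
| 3 | 99.9% | 97.7% |

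With no effect, the >= 1 log10 rate is 25% at SD 1.5 and 31% at SD 2. The any-fall rate stays at 50% whatever the SD. Selecting on a baseline of at least 10^3 CFU/mL adds some regression to the mean: simulated no-effect any-fall rates are 50% to 58% for an assumed mean baseline of 4.5 to 6 log10, and up to 61% at 4.

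The any-fall rate does rise with effect, but it starts near 50% and is close to its ceiling by 2 log10.

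**2. Raw counts as the fallback.** 40,000 simulated trials, 24 vs 12, lognormal counts, active arm truly 1 log10 lower:

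| Assumed log10 SD | 1 | 1.5 | 2 |
|---|---|---|---|
| Largest of 12 patients, median share of arm total | 52% | 69% | 80% |
| Wrong order, arithmetic mean | 6% | 22% | 32% |
| Wrong order, median | 1% | 5% | 11% |
| Wrong order, log10 mean | 0.3% | 3% | 8% |

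With the same effect and SDs for the change, any-fall rates are in the wrong order or tied in about 2% to 16% of trials.

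**3. Precision of the log10 difference.** Half-width of the 95% CI = t(0.975, n1 + n2 - 2) x SD x sqrt(1/n1 + 1/n2). For 24 vs 12 it is 0.72, 1.08 and 1.44 log10 at SD 1, 1.5 and 2. If the PD Population shrinks to 16 vs 8, it is 0.90, 1.35 and 1.80. The interval is wide, but it tells the reader which effect sizes the data allow.

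**4. Time to 1 log (minor).** With a constant 1-log10 effect, the six post-baseline visits and patient/measurement SDs of 0.5/0.5, 1/0.5 and 1/0.7, 71% to 79% of active and 32% to 46% of placebo patients reach 1 log. So 21% to 29% and 54% to 68% have no time, and section 3.5 does not say how they enter the summary.

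**5. Cultures after an antibiotic (conditional).** One patient is 1/12 = 8.3 points on placebo and 1/24 = 4.2 points on active. As an illustration, 8/24 - 2/12 = +16.7 points of elimination becomes 8/24 - 4/12 = 0 if antibiotics clear two placebo failures. But if 25% of each arm take antibiotics before any response and all clear, counting everything gives (8/24 + 0.25 x 16/24) - (2/12 + 0.25 x 10/12) = +12.5. Giving no credit for those clearances gives 0.75 x 16.7 = +12.5. Neither version is an unbiased correction of the other.

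**The case against.** A reader might infer four stronger points. The SAP does not support them.

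- **That the plan rules out any continuous summary of E. coli burden.** Section 3.5 opens by saying that the secondary endpoints will be summarized by treatment, and incidence is introduced with the word also. With section 3.1.4, this leaves room for a descriptive summary, which would include the median. The 6% to 32% figure for raw means is therefore not the risk for someone who reads the median. What stands is that no sentence names such a summary, puts it on a log scale or expresses it as change from baseline.
- **That the 50% floor biases the comparison.** It applies to both arms, and the placebo arm displays it. The fault is lost information.
- **That a 1-log threshold separates the arms better.** At SD 1 the arm difference for any fall is 69 - 50 = 19 points at a true fall of 0.5, and 84 - 50 = 34 at 1. For >= 1 log10 it is 31 - 16 = 15 and 50 - 16 = 34. The threshold gains only at larger effects (at 2 log10: 98 - 50 = 48 against 84 - 16 = 68). Its merit is that it is easier to interpret.
- **That antibiotics contaminate the results and the plan has no rule for it.** Using all post-baseline data already sets a default for the derived parameters. Whether patients are cultured after an antibiotic depends on the protocol, which is not shown. Section 3.2.3 says only that patients who progress to infection are followed for safety.

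It is also fair to say that elimination and time to 1 log do have thresholds, that all E. coli data are listed for 36 patients, and that nothing is tested. This limits the harm. It does not supply the missing summary, and where there is no test the description is the whole result.

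**Conclusion.** The point holds as a recommended change of moderate weight. The SAP names by-visit reduction as an incidence with no minimum size and commits nowhere to E. coli log10 CFU/mL or its change, while it does commit to changes from baseline for five other kinds of measurement. The cost is information: the named rate cannot tell a 2-log10 fall from a 3-log10 fall at SD 1, and the fallback on an unstated scale can be driven by one or two patients.

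The sizes rest on normal log10 counts with assumed SDs of 1 to 2 and assumed mean baselines. The direction does not depend on those choices. The missing summary rule for time to 1 log is minor. The antibiotic question supports no more than an optional sensitivity analysis.

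**What to change.** In section 3.5, before unblinding:

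1. Make log10 CFU/mL and its change from baseline, by visit and arm in the PD Population, the main summary of burden. Give the between-arm difference with a descriptive 95% CI and no test. State the value used for no-growth cultures, because log10 of 0 is undefined.
2. Say that reduction means any value below baseline, if that is meant. Beside that count, report the rate at >= 1 log10, the plan's own threshold, as an aid to interpretation.
3. Minor: summarize time to 1 log over the whole PD Population by Kaplan-Meier, with the number who do not reach it, and not among responders only.
4. Optional, if the protocol takes cultures after antibiotics: add a summary that does not credit falls first seen after a post-baseline systemic antibiotic active against E. coli. Fix the antibiotic list before unblinding, from the coded medications (section 3.3.6) and the isolate resistance data (section 3.6.2.2). State whether such patients are censored or kept at risk. Label it a sensitivity analysis, not a correction.

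The cost is SAP wording and modest programming on data already collected. The >= 1 log10 rates will look lower than the any-fall rates, and the text should say why.

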## 3 STATISTICAL METHODOLOGY

### 3.1 General Considerations

#### 3.1.1 *Definition of Baseline*

Baseline is defined as the last measurement prior to the first dose of study drug unless otherwise specified.

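### Biological elimination starts exactly at the PD Population entry floor and needs only one culture, so a patient near 1×10^3 CFU/mL can be scored as eliminated, and then recurrent, by culture variation alone

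*SAP*

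**What the plan says.** Section 3.2.5 requires, among other conditions, that PD Population patients "have a baseline *E. coli* measurement at or above" 1×10^3 CFU/mL. Under Section 3.1.1, "Baseline is defined as the last measurement prior to the first dose of study drug unless otherwise specified", so this is a single reading and not an average.

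Section 3.5 states "Biological elimination is defined as measurement below" 1×10^3 CFU/mL. Elimination is counted at each scheduled visit, the post-baseline ones being "Day 2, Day 3, Day 5, Day 7 (EOT), Day 14 and Day 28". It is counted again as "Biological elimination at any timepoint", where the "parameters will be derived based on all available post-Baseline data and summarized and listed". On population, Section 3.5 says of the PD endpoints: "These will be summarized by treatment based on the PD Population".

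The same section defines recurrence as a past elimination followed by a count above the patient's own baseline. Recurrence of colonization is a listed secondary endpoint (Section 2.3.2). Elimination itself is not in that list.

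**The concern.** The entry floor and the elimination cut-off touch. A patient who reads 1,000 CFU/mL at baseline and 990 at one later visit is scored as eliminated. The fall is log10(1000/990) = 0.004, although the SAP's own response measure in Sections 2.3.2 and 3.5 is a 1-log fall. A patient starting at 1×10^6 must fall by more than 3 logs for the same label.

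Three features add to this:

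- The any-timepoint line accepts one qualifying culture out of six scheduled visits, plus any other post-baseline data.
- Entry on one reading brings regression to the mean. A patient whose usual count lies below the floor can enter on one high reading and then be scored as eliminated by returning to the usual level.
- Scatter around the floor can also produce a later count above baseline, so an unchanged patient can be reported as eliminated and then recurrent.

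At stake is how to read the elimination and recurrence percentages in a trial of about 24 versus 12 patients before PD exclusions.

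**Working it through.** The SAP states no elimination rate, so there is no figure to reproduce. The check asks how often a patient with no true change would be scored as eliminated.

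**Inputs from the SAP:** cut-off below 1×10^3 (Section 3.5); floor 1×10^3 (Section 3.2.5); six post-baseline visits (Section 3.5); a single-value baseline (Section 3.1.1); 36 patients randomized 2:1 (Section 2.2.4).

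**Assumed, not in the SAP:** single log10 counts are normal around a constant true level, with SD 0.5 (range 0.3–0.7). Cultures are either independent or share a correlation of 0.5, baseline included.

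**Formulas, independent cultures:** P(visit) = Φ((3 − log10 true count)/SD); P(any of 6) = 1 − (1 − P(visit))^6.

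At 2×10^3, log10 = 3.301. With SD 0.5, P(visit) = Φ(−0.602) = 0.274 and P(any) = 1 − 0.726^6 = 0.853. At SD 0.3 the pair is 0.158 and 0.643; at SD 0.7 it is 0.334 and 0.912.

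| True count (CFU/mL) | One visit, SD 0.5 | Any of 6, SD 0.5 | Any of 6, SD 0.3 to 0.7 |
|---|---|---|---|
| 1×10^3 | 50% | 98% | 98% throughout |
| 2×10^3 | 27% | 85% | 64–91% |
| 1×10^4 | 2.3% | 13% | 0.3–38% |
| 1×10^5 | about 0% | 0.02% | about 0–1.3% |

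The 38% at 1×10^4 is Φ(−1/0.7) = 0.077 per visit, then 1 − 0.923^6. The 1.3% at 1×10^5 is Φ(−2/0.7) = 0.0021 per visit, then 1 − 0.9979^6.

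**Correlated cultures** (simulation, patients whose observed baseline is at or above 1×10^3; figures good to about one percentage point): at 2×10^3 the any-visit chance is about 53% (37–60%), and at 1×10^3 about 75%.

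**False recurrence** (scored elimination, then a count above the observed baseline) at 2×10^3 and SD 0.5: about 54% independent, 32% correlated.

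**Adding a 1-log condition alone**, at 2×10^3 and SD 0.5: if baseline were exact, a count at or below 10^2.301 would be needed, so P(visit) = Φ(−2) = 0.023 and P(any) = 1 − 0.977^6 = 0.13. Baseline is one noisy reading, however. Simulating that noise gives about 35% (independent).

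**Adding the 1-log condition and confirmation by the next culture**, SD 0.5, noisy baseline:

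| True count (CFU/mL) | Independent | Correlation 0.5 |
|---|---|---|
| 2×10^3 | 85% falls to about 10% | 53% falls to about 3% |
| 1×10^3 | 98% falls to about 26% | 75% falls to about 7% |

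**Weight of one patient:** 1/12 = 8.3 percentage points on placebo and 1/24 = 4.2 on LBP-EC01, before PD exclusions.

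**The case against.** The strongest reply is that exposure is unknown. Misclassification matters only if patients start near the floor. The SAP gives no baseline distribution, Section 2.2.1 speaks of significant colonization, and the PD Population also requires meeting enrollment criteria that are set in the protocol, which is not at hand. This stands. The 1×10^3 floor shows that such patients are provided for, not that they are common.

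A second reply is that one threshold for colonized and no longer colonized is coherent. The per-visit lines do not carry the six-visit inflation, the relative fall is covered by the reduction and time-to-1-log summaries, and the listings would show a 1,000-to-990 elimination. This also largely stands, and it is why the current line should stay. It does not answer the recurrence problem: that endpoint takes the unconfirmed elimination as its starting event and has no alternative derivation.

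A reader might infer that the rule favours LBP-EC01 or inflates type I error. The SAP does not support that. Culture variation acts in both arms, and Section 3.1.5 plans no formal test. Nor does the SAP make elimination its leading PD claim, since Section 2.3.2 does not list it.

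**Conclusion.** The weakness is real and confined to baselines near the floor. Under the assumed SD and an unchanged true count of 2×10^3, a false elimination at some visit is more likely than not at SD 0.5, whether cultures are independent or moderately correlated. By 1×10^5 it is negligible. A reader might take the 85% or 98% as the expected error rate in this trial; they are not, because they apply only to patients at or just above the floor and assume independent cultures.

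The harm is an inflated background rate in both arms, a diluted contrast, and sensitivity to a chance imbalance of one or two low-baseline patients. It affects descriptive summaries only. A cheap addition is justified; discarding the threshold definition is not.

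**What to change.** In Section 3.5, keep the below-1×10^3 line as written and pre-specify a second line, confirmed elimination:

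- a count below 1×10^3 CFU/mL that is also at least 1 log10 below the patient's baseline, or a culture with no *E. coli* growth; and
- the next available scheduled culture also below 1×10^3 CFU/mL.

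Show patients with no later culture (first qualifying at Day 28, or dropout) as unconfirmed, not as failures or successes. Derive recurrence from confirmed elimination as well as from the current definition. Both conditions are needed, because the 1-log condition alone leaves too much error once baseline noise is counted.

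The cost is SAP wording and one derivation from counts already collected, to be settled before unblinding. The confirmed rate will be lower. Patients with baselines of 1×10^3 to 1×10^4 must reach 1×10^2 to 1×10^3 or show no growth. They can qualify only if the culture quantifies below 1×10^3 or reports no growth. The SAP gives no quantification limit for the culture, so check it first.

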which the patient may be released from the clinic/hospital. The patient will return on Day 14 ( $\pm 3$  days) for the Day 14 Visit, and on Day 28 ( $\pm 3$  days) for the Day 28 Visit. AE data will be collected throughout the study, including Day 28 through Day 35. At Day 35, the patient will be contacted by telephone to assess any AEs or lab abnormalities since the Day 28 Visit. At the discretion of the investigator, the patient may be asked to return to the clinic/hospital for a Day 35 Visit ( $\pm 3$  days). Day 35 is the end of study. Assessments will be conducted as described in Table 1 and Table 2 of the Protocol.

Safety will be assessed throughout the study. Spleen evaluations will include ultrasound assessments for splenomegaly at Day -6 to -1, Day 3, and Day 7 and clinical examinations to assess for splenomegaly will be performed at all visits. In addition, attention will be focused on identifying any progression of a urinary colonization to an active infection, including the signs and symptoms of local vesicular reactions (e.g., bladder pain, hematuria). Symptoms of active infection will be solicited during daily observations throughout the 7 days of treatment and until the end of study. Symptoms of note in this population include dysuria, urinary frequency, urinary urgency, suprapubic discomfort and flank pain in addition to non-specific symptoms of urinary leakage, change in voiding habits, worsening muscle spasm, increasing autonomic dysreflexia, sweating, malaise, and fever or hypothermia. Urine microscopy and culture will be assessed frequently during the study (see Table 2 of the Protocol).

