### 2.3.2 Secondary Endpoints

The secondary endpoints involve summarizing PD parameters of LBP-EC01. These include:

- Reduction in urinary *E. coli* burden at any of the following timepoints: Day 2, Day 3, Day 5, Day 7 (EOT), Day 14, and Day 28
- Time to 1 log reduction in urinary *E. coli* count
- Recurrence of *E. coli* colonization or incidence of infection based on clinical signs and symptoms
- Changes in IgA, IgE, IgG, and IgM levels

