### *3.1.3 End of Study Definition*

A patient is considered to have completed the study if he or she has completed all portions of the study including the last visit or the last scheduled procedure shown in the SoA (Table 1 of the Protocol).

The EOS is defined as the last date that patient safety data is collected (i.e., Day 35). Once patients have completed Day 28, they may resume their regular medications and have any new intermittent catheters re-established as directed by their physician.

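### SAP section 3.5 fixes no method or censoring for its two time-to endpoints and, secondarily, does not separate E. coli falls that follow a non-study antibiotic

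*SAP*

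**What the plan says.** Section 2.3.2 names "Time to 1 log reduction in urinary" E. coli count as a secondary endpoint. Section 3.5 adds biological elimination at any timepoint (below 1 x 10^3 CFU/mL), incidence of and time to recurrence, and incidence of infection. It states that these E. coli "parameters will be derived based on all available post-Baseline data and summarized and listed". Recurrence is "past biological elimination followed by increase above the patient's baseline CFU/mL". Infection is defined as follows: "Incidence of infection based on clinical signs and symptoms defined as an adverse event marked as a UTI symptom and followed by antibiotic use". Reduction and elimination are also counted by visit through Day 28.

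On the population, section 3.2.5 says "The PD Population will be the primary population for analysis of all PD-related secondary and exploratory endpoints". Its entry conditions concern enrollment criteria, dosing and baseline measurements. None concerns antibiotics after baseline.

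The general rules are short. Section 3.1.4 summarises continuous data by "n (number of non-missing values), mean, median, standard deviation, minimum, and maximum", and section 3.1.6 leaves missing data unimputed unless a section says otherwise. No section names a time-to-event method or a censoring rule.

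Infection is foreseen. Section 2.2.1 says "attention will be focused on identifying any progression of a urinary colonization to an active infection", and section 3.2.3 states that patients who progress stop study drug, receive treatment for their symptoms and stay in safety follow-up.

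**The concern.** A time-to endpoint has a value only for patients who reach it. If the others have no value and nothing is imputed, the mean and median describe responders alone. An arm with a few early responders then looks faster than an arm in which many respond over a longer period, so the time summary and the response rate can point in opposite directions. For recurrence the gap is wider. The SAP does not say when the clock starts, or whether the incidence is taken among patients with elimination or among all PD Population patients.

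The second issue is narrower. The section that uses all post-baseline data also builds antibiotic use into its infection definition, but it does not say how counts taken after the antibiotic are treated. Read literally, a fall below the threshold after an antibiotic is an elimination for the assigned arm. The same antibiotic could also suppress the later rise that defines recurrence. Response rates by arm could then mix the effects of study drug and antibiotic, and no summary table would show it.

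**Working it through.** **Inputs from the SAP.** There are 36 patients at 2:1 (section 2.2.4): 36 x 2/3 = 24 active and 36 x 1/3 = 12 placebo. E. coli is summarised on Days 2, 3, 5, 7, 14 and 28 (section 3.5). The SAP gives no response rate, antibiotic rate, power or precision figure, so there is no planned figure to reproduce. All response data below are assumptions chosen to show what the rules can do.

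**Time to 1 log reduction (assumed data, no antibiotics).** Placebo: 4 of 12 respond, on Days 2, 2, 3 and 7. Active: 16 of 24 respond, 5 on Day 2, 3 on Day 3, 5 on Day 5 and 3 on Day 7. All others are followed past Day 7 without the event.

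- Responders only, placebo: the middle values are 2 and 3, so the median is (2 + 3)/2 = 2.5 days.
- Responders only, active: the 8th and 9th of 16 values are 3 and 5, so the median is (3 + 5)/2 = 4 days.

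Kaplan-Meier in all patients, proportion still without the event:

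| After | Placebo | Active |
|---|---|---|
| Day 2 | 10/12 = 0.833 | 19/24 = 0.792 |
| Day 3 | 9/12 = 0.750 | 16/24 = 0.667 |
| Day 5 | 9/12 = 0.750 | 11/24 = 0.458 |
| Day 7 | 8/12 = 0.667 | 8/24 = 0.333 |

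The placebo median is not reached; the active median is Day 5. The proportions responding are 4/12 = 33% (Clopper-Pearson 95% CI 9.9 to 65.1) and 16/24 = 67% (44.7 to 84.4). The responders-only medians favour placebo, and the all-patient summary favours active.

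**Recurrence denominator (assumed).** Suppose 3 of 12 placebo patients reach elimination and 1 of them recurs. The incidence is 1/3 = 33.3% among patients with elimination and 1/12 = 8.3% among all. If one further patient is cleared by an antibiotic and does not rise later, the first becomes 1/4 = 25.0% and the second stays 8.3%. The SAP does not say which applies.

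**Falls after an antibiotic.** One reclassified patient moves a rate by 1/12 = 8.3 points (placebo) or 1/24 = 4.2 points (active) if all 36 enter the PD Population. With an assumed 8 and 16 patients, the steps are 1/8 = 12.5 and 1/16 = 6.25 points. Taking assumed rates of 12/24 and 3/12, the difference is 50.0 - 25.0 = 25.0 points. One antibiotic clearance on placebo gives 50.0 - 33.3 = 16.7 points; one on active gives 54.2 - 25.0 = 29.2 points. The direction depends on which arm the patient is in.

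**Search for a rule elsewhere.** The Evaluable Population (3.2.3) serves non-PD endpoints only, and it keeps progressors who were dosed per protocol for the first 4 days. The named subgroups (3.2.6) and the optional COVID-19 analyses (section 6) do not separate patients by antibiotic use. The medication-date rules in 3.3.6 only sort prior from concomitant use.

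**The case against.** The SAP nowhere says that a fall after an antibiotic is a response. In section 3.5 the all-data wording follows a list of fixed visit days and may only mean that every assessment is used. This stands in part: the conclusion follows from a rule stated without exception, not from an explicit instruction. Using all data regardless of antibiotics is also a legitimate strategy, and the missing label alone would be minor.

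The antibiotic point depends on cultures continuing after the antibiotic starts. Section 3.2.3 promises safety follow-up only, and the protocol schedule is not shown. Section 3.1.3 says "Once patients have completed Day 28, they may resume their regular medications", which suggests medication limits up to the last listed culture day. These are real limits, although they do not rule out antibiotic treatment of an infection.

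Much can be traced already. Infection followed by antibiotic use has its own summary, concomitant medications are tabulated by class and arm, and all E. coli data are listed. That lowers the severity, but the reader must still match patients by hand.

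On the time-to endpoints, responders-only is an inference from defaults that apply generally. The n would be shown, the visit-wise counts give reduction and elimination by day (though not 1 log reduction), and section 8 leaves programming detail to a separate document. The example was also constructed to show a reversal. It shows what can happen and does not predict this trial. Even so, the choice of estimator and censoring belongs in the SAP.

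**Conclusion.** The point holds, at low to moderate severity. The firmer part is the time-to endpoints: the only summary that the SAP supplies would, by inference, describe patients with the event and could rank the arms opposite to the proportion responding. This part needs no antibiotic use and does not depend on the protocol schedule.

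The antibiotic part is secondary and conditional. Each affected patient moves a rate by 8.3 or 4.2 points if all 36 enter the PD Population, and by more if fewer do. The number affected is unknown.

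A reader might infer that the plan deliberately credits antibiotic clearances to study drug, or that it favours one arm. The document supports neither: the handling is unstated, and the bias can run either way. Nor is this a type I error or power problem, since section 3.1.5 tests no hypothesis.

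**What to change.** In section 3.5:

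- (a) Summarise time to 1 log reduction by Kaplan-Meier in all PD Population patients, from first dose. Censor patients without the event at their last E. coli assessment. Report the number and proportion with the event and a 95% CI.
- (b) Summarise time to recurrence by Kaplan-Meier among patients with elimination, from the first assessment that meets it, censored at the last E. coli assessment. State the denominator for incidence.
- (c) Keep the all-data summaries and state that they are regardless of antibiotic use. Add one companion. For reduction, 1 log reduction and elimination, count assessments after the start of a non-study antibacterial active against E. coli as non-response. For recurrence, restrict the risk set to elimination reached before any such antibacterial, and report the composite of recurrence or start of such an antibacterial after elimination.
- (d) Before unblinding, alongside the Evaluable Population list, finalise the affected patients, the antibacterials counted as active, and the handling of any incomplete start dates. Do not substitute the adverse event onset for an incomplete antibiotic start date: the antibiotic follows the symptom, so onset can fall too early and turn responses from before the antibiotic into failures.

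The cost is SAP wording, a few extra tables and a blinded review of medications. The companion response rates may be lower than the all-data rates.
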